12.1.1 Electronic Hospital records (EHR)

No study-related access to the patient's electronic hospital record (EHR) will occur before informed consent for study participation has been obtained.

Parents will be asked to consent to EHR access for the purposes of planning and conducting follow-up visits, admissions, and surgery, and for collection of relevant study data. This includes permission to:

- retrieve participant-related data and review clinical documentation related to outpatient visits, admissions, surgical procedures, and any adverse events (AEs);
- access and review radiographic imaging; and
- maintain EHR access until completion of the study.

By providing consent, parents authorize the Principal Investigator (PI) and relevant authorities to access information in the patient's medical record for the purpose of conducting the study and for oversight activities, including self-inspection, quality control, and monitoring, as required.

The patient's hospital records are stored securely in the hospital EHR system (Epic Systems Corporation, Verona, Wisconsin, USA).

12.1.2 Electronic CRF

For this study, an electronic case report form (eCRF) has been designed to accommodate the specific features of the study design. Access to the eCRF is password protected and role-based, with functions assigned according to user responsibilities. The eCRF will be completed in a timely manner after each participant visit or other documentable event, typically within 7 days.

In general, data recorded in the hospital patient record are considered source data. Data collected through participant- and investigator-completed electronic questionnaires are also regarded as source data.

The eCRF is stored securely using Research Electronic Data Capture (REDCap; Vanderbilt University, USA), hosted by the Capital Region of Denmark.

12.2 Imaging data

Radiographs are stored securely in the hospital's Picture Archiving and Communication System (PACS). For the blinding process, radiographs provided for outcome assessment will be de-identified and will not contain patient-identifiable information. The images will be labeled only with the participant's numeric study identifier code.

12.3 Confidentiality

Participant privacy and confidentiality will be maintained throughout the study. The eCRF and all other study documents transferred to the sponsor will be de-identified and will contain only the participant's numeric study identifier code. The study site will maintain the linkage between the study identifier code and the participant's identity.

Fully identifiable information may be reviewed for the purpose of source data verification and confirmation of eCRF entries only at the study site. Such review may be performed by the sponsor or the sponsor's designee, regulatory authorities, or quality assurance personnel, in accordance with applicable site-specific regulations and procedures. Personal medical information will be treated as confidential at all times.

The informed consent materials will describe confidentiality safeguards and will include permission for authorized access to relevant medical information for study conduct and oversight purposes.

13 Study management and quality control

13.1 Contract Research Organization

No Contract Research Organization (CRO) will be engaged for this clinical investigation.

13.2 Training and organization at the study site

Prior to enrolling the first participant, Sub-Investigators (SIs) and study coordinator(s) (SCs) will receive study-specific training. Training will cover the CIP procedures, inclusion and exclusion criteria, eCRF completion, and relevant requirements under ISO 14155 and ICH-GCP. Training will be conducted by the Principal Investigator (PI). In the event of changes in study site personnel, new staff will undergo the same training prior to performing any study-related tasks.

The PI holds current GCP (or equivalent) training/certification.

An Investigator Site File (ISF) will be maintained at the study site and will contain all essential study documents.

The PI is responsible for overall supervision of the study and will provide direction, oversight, and training to delegated research personnel as required.

14 Monitoring and safety oversight

An independent monitor will be appointed before enrolment of the first participant. The monitor will be independent of both the research group and the Department of Orthopedic Surgery and may be based in another department at Copenhagen University Hospital - Herlev and Gentofte, or in another appropriate hospital unit. The monitor will have no role in recruitment, informed consent discussions,

treatment allocation, postoperative outcome assessment, radiographic endpoint evaluation, or statistical analysis.

Monitoring will be performed according to a written monitoring plan and will focus on trial-critical processes and data, including informed consent documentation, eligibility, randomization, device traceability/accountability, source data verification for the primary endpoint, protocol deviations, and the completeness and timeliness of SAE/SADE reporting. Monitoring findings will be documented in written monitoring reports, and any corrective and preventive actions will be followed to resolution by the Principal Investigator and sponsor.

Clinical safety oversight remains the responsibility of the Principal Investigator and sponsor as described in Sections 11 and 19. Any monitoring finding considered relevant to participant safety or data integrity will be communicated without undue delay to the sponsor and Principal Investigator.

15 Regulatory affairs

The Clinical Investigation Plan (CIP), associated documents, investigator financial disclosures, and the participant information and informed consent forms (ICFs) will be submitted to the relevant ethics committee (EC) for review and approval. The EC will be kept informed of study progress and relevant events in accordance with its regulations and procedures.

If additional regulatory approvals are required, the study will commence only after all necessary approvals have been obtained from the appropriate authorities.

16 Ethics

As described in Section 9, the risks associated with surgical treatment of pediatric diaphyseal forearm fractures are inherent to standard clinical care. Participation in this study is not expected to materially increase treatment-related risk. The incremental burdens of participation are primarily additional follow-up visits and radiographs; the additional radiation exposure is minimal, and follow-up procedures are designed to support both patient safety and robust outcome assessment.

The study addresses a clinically relevant question: whether bioabsorbable intramedullary nails (BIN) provide an acceptable (non-inferior) time to radiographic healing compared with titanium elastic intramedullary nails (TEN).

The ethical balance of this trial includes a patient-relevant trade-off: potential avoidance of a second implant removal operation versus the possibility of delayed healing and/or delayed return to higher-risk activities. To ensure this trade-off is communicated transparently and reflects family priorities, parents from the pilot cohort reviewed the information materials and contributed acceptability input on the maximum additional weeks of activity restriction they would consider acceptable.

The study will be conducted in accordance with the principles of the Declaration of Helsinki and applicable requirements under ICH-GCP and ISO 14155. Participation is voluntary. Parents and children will be informed that they may withdraw consent at any time without consequences for the child's current or future medical care. Children will be informed in an age-appropriate manner, and

assent will be obtained when appropriate. Participant confidentiality and data protection will be ensured as described in Section 12.

We acknowledge that longer-term registry-based follow-up could provide valuable supplementary information on later healthcare utilization and complications related to the two treatment strategies, including implant removal procedures, reoperations, refracture, and other late healthcare contacts. An approximately 5-year registry-based follow-up is therefore considered scientifically relevant. However, such follow-up is not part of the present active study period and will only be undertaken following a separate protocol amendment and any required ethics, data protection, and registry approvals.

17 Patient insurance

As with all treatment provided within the Danish healthcare system, all participants are covered by the Danish Patient Compensation Association (Patienterstatningen).

18 Study report and publication policy

18.1 Final Study Report

The results of the statistical analyses will be summarized in a statistical report, which will form the basis for the comprehensive Final Study Report (FSR). The comprehensive FSR will serve as the primary source document for subsequent publications.

18.2 Publication

The publication strategy will be agreed between the sponsor and the Principal Investigator (PI), and any other relevant parties.

This Clinical Investigation Plan (CIP) may be submitted for publication in a peer-reviewed international journal.

The study will be reported to the European database on medical devices (EUDAMED) in accordance with the Medical Device Regulation (EU) 2017/745, as applicable.

The final study results—including positive, negative, and inconclusive findings—will be submitted for publication in a peer-reviewed international orthopedic journal and may also be presented at national and international scientific meetings.

If publication in a peer-reviewed journal is not achieved within a reasonable period after completion of the Final Study Report, the results will instead be made publicly available through an alternative publicly accessible channel, such as a preprint server and/or an institutional or sponsor repository

19 Termination criteria

Study progress, including recruitment and safety aspects, will be closely monitored in collaboration with the sponsor. The sponsor may decide to terminate the study for reasons defined in Section 19.1. In the event of early study termination, all participants already enrolled will, where feasible, continue follow-up until the final follow-up visit as defined in this CIP.

19.1 Stopping rules

To identify potential safety signals or unexpected complications, an interim safety review will be performed after approximately 50% of the planned randomized participants have reached the 12-week follow-up visit (or have achieved radiographic healing, whichever occurs first).

The interim safety review will be conducted by the PI in collaboration with the sponsor and will include review of adverse events (AEs), adverse device effects (ADEs), serious adverse events (SAEs), serious adverse device effects (SADEs), and key clinical outcomes (refracture, deep infection, reoperation, loss of reduction, delayed union). If predefined stopping criteria are met, recruitment will be temporarily paused while the events are reviewed and appropriate actions are taken (including notification of the ethics committee, as applicable).

This interim review is for **safety monitoring only** (AEs/ADEs/SAEs/SADEs and prespecified healing-related safety signals including refracture and delayed healing) and is not a formal interim analysis of the primary noninferiority hypothesis; no early stopping for noninferiority/superiority efficacy is planned, and no alpha-spending adjustment will be applied based on this safety review.

Recruitment will be put on hold for safety reasons if at least one of the following incidents occurs and is assessed as possibly related to the investigational device (BIN):

- Refracture: An absolute refracture rate >25% (within the study follow-up period) will not be tolerated and will constitute a criterion for pausing recruitment.
- Delayed healing: An observed mean time to radiographic healing >12 weeks in the investigational (BIN) group will constitute a criterion for pausing recruitment.

After review, the sponsor and PI will decide whether recruitment can resume unchanged, resume with protocol modifications/risk-mitigation measures, or whether the study should be terminated.

20 Disclosures and economy

The initiative for this study has been taken solely by the authors.

The authors and affiliated colleagues have not received financial payments or other benefits from any commercial entity related to the subject of this study. The authors declare that they have no conflicts of interest.

Participants will not receive any financial compensation, gifts, or other economic benefits for participation in this study.

21 Deviations from the Clinical Investigation Plan

Deviations from the procedures described in this CIP, or changes to the CIP without following the defined process, are not permitted.

A CIP deviation is any non-adherence to the protocol that does not involve eligibility (inclusion/exclusion criteria), the primary endpoint, or compliance with GCP/ISO 14155 requirements. Deviations are

considered minor and are not expected to have a major impact on participant safety or data integrity. Deviations will be documented and reported to the sponsor within 10 working days.

A CIP violation is any significant divergence from the protocol by the participant, investigator, sponsor, or other responsible party that may affect, for example, eligibility (inclusion/exclusion criteria), the primary endpoint, or compliance with GCP/ISO 14155 requirements. The sponsor must be notified within 5 working days of becoming aware of the violation. Violations will be documented at the study site and recorded in the eCRF.

22 Amendments to the Clinical Investigation Plan

No changes to the approved CIP are permitted except where necessary to eliminate an immediate hazard to participant safety or where changes are purely administrative or logistical and do not affect participant safety or the scientific validity of the study. Any urgent change implemented to protect the life, health, or well-being of enrolled participants will be reported to the relevant bodies in accordance with applicable requirements, and no later than 5 days after implementation.

If changes to this CIP become necessary during study conduct, a formal amendment will be prepared, issued, and submitted for approval and/or notification to the relevant ethics committee and other required authorities, as applicable, prior to implementation.

23 Time schedule

Ethics Committee approvals	2.2026	to	05.2026
First patient/first visit			05.2026
Last patient/first visit			05.2029
Last patient/last visit			05.2031
Data analysis	06.2031	to	12.2031
Final Study Report	01.2032	to	03.2032

24 Authors

CIP developed by

PI	[name] Department of Orthopedic Surgery Copenhagen University Hospital - Herlev and Gentofte, Copenhagen, Denmark
Additional author(s)	[name], ph.d., professor [name], ph.d.

CIP approval signatures

Name	Function	Date	Signature
[name]	Principal Coordinating Investigator		

25 Reference list

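### Under Section 19.1 a crossed safety threshold need not pause recruitment, because the hold also needs a relatedness judgement that is undefined for a mean and unclear for a rate

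*Protocol*

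**What the plan says.** All the relevant text on the hold is in Protocol Section 19.1.

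- **Timing and conduct.** The interim safety review takes place "after approximately 50% of the planned randomized participants have reached the 12-week follow-up visit", or have healed if that comes sooner. On who does it: "The interim safety review will be conducted by the PI in collaboration with the sponsor".
- **Order of events, second paragraph.** "If predefined stopping criteria are met, recruitment will be temporarily paused while the events are reviewed and appropriate actions are taken".
- **Sentence introducing the criteria.** Recruitment goes on hold "if at least one of the following incidents occurs and is assessed as possibly related to the investigational device (BIN").
- **Refracture bullet.** "An absolute refracture rate >25% (within the study follow-up period) will not be tolerated and will constitute a criterion for pausing recruitment". No treatment group is named.
- **Healing bullet.** "An observed mean time to radiographic healing >12 weeks in the investigational (BIN) group will constitute a criterion for pausing recruitment".
- **Closing sentence.** "After review, the sponsor and PI will decide whether recruitment can resume unchanged", resume with modifications, or end in termination.

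Elsewhere, Section 11.2 lists relationship to the device among the items collected for each adverse event. Section 11.5 has a medical expert review how adverse events are classified.

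**The concern.** A numerical pause criterion is useful because it limits discretion: the number is reached, recruitment stops, and the causes are examined while no further children are enrolled. The introductory sentence of Section 19.1 places a judgement in front of the number. Someone must first assess the incident as possibly related to BIN, which is part of what the pause is meant to give time for.

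The condition also does not fit what it is attached to. Relatedness is a property of a single event. The two incidents are summary figures, a rate and a mean, and the section does not say how either is assessed for relatedness, by what standard, or whether recruitment continues meanwhile.

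These are the only two numerical criteria for pausing recruitment in the protocol. Two people applying the section in good faith to the same data could act differently, and one of them would keep randomizing children aged 3 to 13 with a threshold crossed, without breaching the protocol.

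**Working it through.** **1. The sentences side by side.**

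| Part of Section 19.1 | What starts the hold | Order |
|---|---|---|
| Second paragraph | Predefined criteria met | Pause while events are reviewed |
| Introductory sentence | Incident occurs **and** is judged possibly related to BIN | Judgement, then hold |
| Two bullets | The threshold is itself a criterion | Not stated |
| Closing sentence | Not stated | Review, then decision to resume or stop |

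The introductory sentence is conjunctive, so a crossed threshold alone does not meet it. Nothing else in the section says that the hold applies when the relatedness judgement is negative or still open.

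**2. Does the condition have a value for each criterion?**

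- *Mean healing time above 12 weeks.* Relatedness is recorded per adverse event (Section 11.2). A group mean has no entry there, and Section 19.1 gives no rule for judging one. The condition is undefined.
- *Refracture rate above 25%.* Each refracture can carry a relatedness entry. The text does not say whether the numerator is all refractures or only related ones, or whether one judgement is made on the rate as a whole.

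**3. How little it takes to change the outcome.** Section 19.1 gives no operating characteristics, so there is no figure of the plan to reproduce.

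Inputs: 60 children in total, 30 per group (Section 8.2.7); 1:1 allocation (Section 6.3.5); review at about 50% (Section 19.1).

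- Children at the review: 0.50 × 60 = 30, so about 30 / 2 = 15 on BIN. The split is an assumption.
- Smallest count above 25%: 0.25 × 15 = 3.75, so 4 refractures.
- All four count: 4/15 = 26.7%, threshold crossed.
- One judged unrelated and only related cases count: 3/15 = 20%, not crossed.
- One judgement made on the rate as a whole and found unrelated: no hold, whatever the rate.

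**4. Illustration only.** Let X be the number of refractures that count, binomial with n = 15 and probability p × q, where p is the true BIN refracture rate and q the share judged related. Then P(X ≥ 4) is:

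| p | q = 1 | q = 0.75 | q = 0.5 | q = 0.25 |
|---|---|---|---|---|
| 0.30 | 0.703 | 0.446 | 0.177 | 0.022 |
| 0.40 | 0.909 | 0.703 | 0.352 | 0.056 |

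If relatedness is instead a single judgement on the crossed rate, made positively with an assumed probability of 0.75 or 0.5, then at p = 0.40 the chance of a hold is 0.75 × 0.909 = 0.682 or 0.5 × 0.909 = 0.455. The documents supply neither p, nor q, nor that probability.

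**The case against.** The best defence reads the section as a whole. The second paragraph contains no number; it refers to predefined criteria, and those are set out later, introductory sentence included. Each bullet calls its threshold a criterion and does not say that it is the only condition. On that reading the trigger is threshold plus possible relatedness, followed by pause, review and decision. An initial relatedness entry can exist before any pause, because Sections 11.2 and 11.5 provide for one per adverse event. Possibly related is also a low bar.

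Much of this stands, and it rules out four stronger readings that a reader might infer:

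- *That the section flatly contradicts itself on order.* It can be partly reconciled as above. The fault is that it does not separate an initial assessment from the later review.
- *That the unblinded PI and the sponsor hold the relatedness judgement.* The sentence names no assessor. The PI and sponsor conduct the interim review and decide on resumption, but a medical expert reviews event classification. Section 6.3.7 gives the PI as an example of unblinded staff and does not mention the sponsor.
- *That a comparison with TEN is excluded.* Section 19.1 requires none, but nothing prevents one.
- *That the probabilities in the working measure the loss of protection.* They rest on assumed rates and shares. A share as low as 25% is extreme under so permissive a standard, and the table covers only the reading in which individual cases are filtered.

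The defence does not supply a meaning for the relatedness of a mean, or a numerator for the rate. The low bar also cuts the other way: if the condition is almost always met, removing it costs almost nothing; if it can block a pause, it weakens the threshold.

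**Conclusion.** The point holds in this form. Section 19.1 makes the hold depend on a crossed threshold and a relatedness judgement together, while its bullets present the threshold alone as grounds for pausing. The judgement is undefined for the mean and ambiguous for the rate. Followed as written, a crossed threshold need not pause recruitment.

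This conclusion comes from the wording and needs no assumed rate. The worked example needs only the assumption of about 15 BIN children at the review: one reclassified case moves the rate from 26.7% to 20%.

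The defect also lies in the protocol itself. A recruitment hold is a rule of conduct, whereas the statistical analysis plan announced in Section 8.3 is for the analysis. It should be corrected before enrolment begins.

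**What to change.** Reconcile the sentences of Section 19.1 into one trigger and leave the 25% and 12-week values as they are.

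1. Remove the relatedness condition from the sentence that introduces the criteria.
2. Name the BIN group in the refracture bullet. The phrase being removed is the only text that now ties that criterion to BIN; without this step, pooled or TEN refractures could trigger the hold.
3. Make relatedness, with the TEN figures alongside, an item of the review held during the pause and an input to the decision to resume unchanged, resume with changes, or terminate.

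Possible wording: *Recruitment is paused if the refracture rate in the BIN group exceeds 25% or the mean time to radiographic healing in the BIN group exceeds 12 weeks. During the pause, the review considers whether the finding may be related to the device, with the corresponding TEN figures alongside.*

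The cost is a wording amendment to one section and an occasional temporary pause that the review then lifts. Sample size and primary analysis are unaffected.

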6.2.17 Premature study termination

A participant's involvement in the study may end prematurely (discontinuation of study participation) and/or the participant may discontinue the allocated treatment while remaining in study follow-up.

Reasons may include, but are not limited to:

- Withdrawal of informed consent (for study participation and/or use of data)
- Protocol deviation/violation with potential impact on participant safety or data integrity
- Refracture and/or reoperation (e.g., infection, implant-related complication)
- Investigator's decision (e.g., noncompliance with study procedures, safety concerns)
- Sponsor's decision (e.g., early study termination, safety signal, or regulatory request)
- Lost to follow-up
- Death

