6.2.17.2 Handling of data and missing assessments (interval-censored primary endpoint)

Data collected prior to discontinuation will be retained and used in analyses in accordance with applicable law and the scope of consent. If consent for use of data is withdrawn, previously collected data will be handled in accordance with regulatory requirements (e.g., retention of essential safety data where required) and the participant's stated wishes.

The primary endpoint (time to radiographic healing) will be analyzed as an interval-censored time-to-event outcome. For participants with radiographs demonstrating "not healed" followed by "healed," the event time will be considered to occur within the interval between the date of the last radiograph showing "not healed" and the date of the first radiograph showing "healed."

If a participant has no radiograph demonstrating healing, the observation will be right-censored at the date of the last evaluable radiograph/assessment.

If a participant undergoes reoperation, experiences refracture, or otherwise has a clinical course that precludes further valid assessment of healing, follow-up will be censored at the date of the last evaluable radiograph prior to that event, unless the event is pre-specified as a competing event in the Statistical Analysis Plan.

Assumptions and handling of missing radiographs (including sensitivity analyses for potentially informative missingness) will be pre-specified in the Statistical Analysis Plan.

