7.1.1.1 Definition of time-to-healing (primary time origin)

Time-to-healing will be defined as the time from the date of surgery/randomization (Day 0) to the first postoperative radiographic assessment meeting the pre-specified healing threshold in all fractured bones. For patients with fractures of both radius and ulna, the endpoint is met when the healing threshold is achieved for both bones; for isolated single-bone fractures, the endpoint is met when the fractured bone reaches the threshold. Injury date will be recorded for all participants. As sensitivity analyses, time-to-healing will also be calculated from the date of injury, and analyses may adjust for the injury-to-surgery interval to assess robustness.

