7.2.6.4 Re-operation

Re-operation risk is anticipated at 0.1-0.5% due for any reason following the procedure.

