8.2.6 Drop rate / sample size inflation

In our pilot study, 1/18 (~5%) participants were lost to follow-up. For the present RCT we apply a total inflation of 10%, comprising ~5% loss to follow-up/withdrawal and ~5% intercurrent events affecting the primary endpoint (e.g., healing-related reoperation). Although intercurrent events will be handled in the primary estimand strategy (see Section 8.3), they reduce the number of informative observations for time-to-union and are therefore accounted for in the sample size inflation.

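### The delayed-healing pause rule in 19.1 rests on a mean of observed healing times, so BIN children reoperated before union drop out of it and it fires less often as such failures increase

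*Protocol*

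**What the plan says.** Section 19.1 of the protocol plans one safety review, when about half of the randomized children have reached 12 weeks or healed. Recruitment is put on hold if one of two numeric criteria is met and judged possibly related to the BIN device:

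- Refracture: "An absolute refracture rate >25% (within the study follow-up period) will not be tolerated".
- Delayed healing: "An observed mean time to radiographic healing >12 weeks in the investigational (BIN) group will constitute a criterion for pausing recruitment".

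The review also looks, without thresholds, at adverse events and at "key clinical outcomes (refracture, deep infection, reoperation, loss of reduction, delayed union").

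Section 19.1 does not say what a child without an observed union contributes to the mean. Other sections bear on this but are not linked to it:

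- Section 7.1.1.1: healing time runs "to the first postoperative radiographic assessment meeting the pre-specified healing threshold in all fractured bones". A child who never meets the threshold has no such time.
- Section 6.2.17.2: after a reoperation or refracture, follow-up is "censored at the date of the last evaluable radiograph prior to that event, unless the event is pre-specified as a competing event". Sections 8.3.8 and 8.3.10 also censor, and 8.3.10 rules out imputing union times. All three are written for the primary endpoint analysis.
- Section 6.2.17: "the participant may discontinue the allocated treatment while remaining in study follow-up". A reoperated child could therefore still be seen to heal later.
- Section 8.3.8: a sensitivity analysis, for the final analysis only, counts healing-related reoperation as not united.

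**The concern.** Delayed union is the protocol's own worry about the more flexible nail (sections 1 and 2), and this trigger is its numeric guard against it. Scheduled films fall at 12 weeks and next at 24 weeks. Unscheduled films aside, a mean of observed times can exceed 12 only through children first seen healed at 24 weeks or later. Reoperating a slow healer before that film removes exactly such a child. The numeric rule therefore weakens as failures of this kind accumulate. For reoperation before union for a reason other than refracture, no other number in 19.1 takes its place.

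**Working it through.** **Planning figures.** Section 19.1 gives no operating figure to reproduce. The planning inputs do reproduce. With SD 3, margin 3, one-sided 0.025 and 90% power (8.2), n = 2(1.960 + 1.282)² × (3/3)² = 21.02, rounded up to 22 per group; 22/0.90 = 24.4, rounded up to 25. Both match 8.2.7.

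**Inputs.** Half of 60 children at 1:1 gives about 15 BIN children at the review. Mean 8 weeks and SD 3 come from 8.2.2. A mean of 11 is the planning mean plus the 3-week margin. Films are at 2, 4, 6, 8, 10, 12 and 24 weeks (6.2).

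**Three readings of the mean.** (a) Children without an observed union are left out, the literal reading. (b) They enter at their censoring time. (c) They stay in follow-up and enter at the first film showing union.

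**Worked case.** Ten of 15 children unite at a mean of 8 weeks; five are reoperated at week 4 for reasons other than refracture.

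- (a) 80/10 = 8.0 weeks: no pause.
- (b) (80 + 5×4)/15 = 6.7 weeks: no pause.
- (c) first seen healed at 24 weeks, (80 + 5×24)/15 = 13.3 weeks: pause.

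Now let the five be non-unions, not reoperated, each with a 24-week film. Under (a) the mean is still 8.0. Under (b) each enters at 24 weeks, giving 13.3 and a pause. So (a) and (b) part company for non-union but not for reoperation before the 24-week film.

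**Simulation.** 200,000 BIN groups of 15, T normal with SD 3, observed time = first film at or after T. With 60 children accrued evenly over 36 months, the first 30 take 18 months, so at the review (18 months − 12 weeks)/18 months = 85% are past 24 weeks. Monte Carlo standard error is at most √(0.25/200,000) = 0.1 percentage points.

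True mean 11, where P(T > 12) = 1 − Φ(1/3) = 0.369. The rule can fire although 11 is below 12 because these children are recorded at 24 weeks.

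| Share of children unhealed at 12 weeks who are reoperated | P(mean > 12), (a) or (b) | (c) |
|---|---|---|
| 0 | 94% | 94% |
| 1/4 | 85% | 94% |
| 1/2 | 67% | 94% |
| 3/4 | 36% | 94% |
| all | 0% | 94% |

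If 50% to 100% of children have a 24-week film, the 94% becomes 74% to 97%; the 0% stays. Log-normal times at shares 0, 1/2 and all give 91%, 61% and 0%.

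True mean 8, children reoperated at week 4:

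| Early reoperation | (a) | (b) | (c) |
|---|---|---|---|
| 0 | 4.0% | 4.1% | 4.0% |
| 5% | 4.4% | 2.8% | 12% |
| 10% | 4.8% | 1.8% | 23% |
| 1/3 | 7.2% | 0.2% | 82% |

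True mean 8, persistent non-union under (b): P(mean > 12) is 4%, 12%, 23%, 51% and 82% at 0, 5%, 10%, 20% and one third non-union. Entered that way, non-union does drive the trigger.

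**The case against.** Four objections carry weight.

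- *The scenarios are extreme.* The protocol states "Re-operation risk is anticipated at 0.1-0.5% due for any reason following the procedure" and allows about 5% for "intercurrent events affecting the primary endpoint (e.g., healing-related reoperation"). In its BIN pilot of 18 children all fractures healed (4.6). At a 5% rate, the chance of 5 or more reoperations among 15 is 0.06%. This stands as a limit on size. It does not remove the point, because a pause rule exists for the case where expectations fail.
- *A cluster of reoperations would be seen.* The review covers reoperation and delayed union, many reoperations would meet the SAE definition (11.1.2), and refracture has its own trigger, reached at 4 of 15. This stands too. What is left uncovered by any number is reoperation before union for other reasons, and non-union when such children are left out.
- *The mean could be model-based.* An interval-censored Weibull mean does respond to censoring: in an example with 10 healers and 5 censored at week 12 it rose from 7.0 to 9.8 weeks. But 19.1 specifies an observed mean.
- *Counting detail can sit in the SAP.* How such children enter a descriptive mean could be stated there, and its absence alone would not be a finding. The point is that the criterion 19.1 fixes is a poor one for this kind of failure.

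A reader might infer that children who never unite cannot raise the mean under any censoring approach. The documents do not support that: 6.2.17.2 and 8.3.10 censor at the last evaluable film, and a 24-week film entered as a value raises the mean. The claim holds for non-union only when such children are left out.

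**Conclusion.** The point holds, at minor to moderate weight. As worded, the trigger is a mean over children with an observed union, and its chance of firing falls as slow healers are reoperated: 94%, 67% and 0% at a true mean of 11 weeks when none, half and all of the children unhealed at 12 weeks are reoperated. Entering censoring times instead does not help for children reoperated before the 24-week film. At rates near those the protocol expects the effect is small: at 5% early reoperation and mean 8 the readings lie between about 3% and 12%.

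The figures assume 15 BIN children, normal times with SD 3, the scheduled film grid and even accrual. The documents do not show that the trial lacks safety oversight for these children. What they lack is a numeric criterion that counts them.

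**What to change.** Keep the mean trigger and add to 19.1: recruitment is also paused if, at the review, 5 or more of about 15 BIN children are not united at 12 weeks, counting any child reoperated before union as not united. The sensitivity analysis in 8.3.8 already classifies reoperation this way, and the data are already collected. The cut-off is the sponsor's choice.

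P(pause) with either rule, reading (a):

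| Scenario | Now | Cut-off 4 | Cut-off 5 | Cut-off 6 |
|---|---|---|---|---|
| Mean 8, no reoperation | 4.0% | 5.5% | 4.1% | about 4% |
| Mean 8, 5% early reoperation | 4.4% | 15% | 6.7% | 4.7% |
| Mean 11, all unhealed at 12 weeks reoperated | 0% | 86% | 70% | 50% |

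The last row at cut-off 5 is the exact binomial P(X ≥ 5), n = 15, p = 0.369, which is 0.705.

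Because the count is added and not substituted, the chance of a pause cannot fall below the present rule. The cost is protocol wording and more temporary pauses when early reoperation is common: at mean 8 and cut-off 5, 14% against 5% at a 10% rate and 40% against 6% at 20%. A pause leads to review and does not by itself end the trial.
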